2.3. Benefit/Risk Assessment

The patient in active drug may benefit in reduction of pain medication's intake.

In terms of risk, safinamide is approved by both EMA and FDA.

When drawing blood samples, bruising might occur.

A detailed description of the chemistry, pharmacology, efficacy, and safety of safinamide is provided in the Summary of Product Characteristics (SmPC).

3. Objectives and Endpoints

| Objectives | Endpoints |
|------------|---|
| Primary | 
 To evaluate the potential efficacy of safinamide 100 mg od, compared to placebo, as add-on therapy, for PD related chronic pain. |
| Secondary | 
 The percentage of pain responders Clinical Global Impression for pain Patient Global Impression for pain Reduction of pain drugs Mood Motor and non-motor symptoms Safety & Tolerability |
| | 
 The change from baseline to week 16 in pain severity (“average worst pain experienced in the last 7 days”), as assessed by an 11-point Numerical Rating Scale (NRS). Participants with reduction in pain severity of ≥ 2 points (“average worst pain experienced in the last 7 days”), at week 16 as assessed by an 11-point NRS, compared to baseline. The CGI-S score for pain at week 16. The change from baseline to week 16 in the CGI-C score for pain. The change from baseline to week 16 in the PGI-C score for pain. The percentage of reduction in number of concomitant pain drugs from baseline to week 16. The number of patients with at least one intake of PRN pain medication. Amount of PRN pain medication The change from baseline to week 16 in the HADS score. The change from baseline to week 16 in the MDS-UPDRS (total score and subscores) during the “ON” phase. Descriptive |

4. Study Design

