6.5. Concomitant Therapy

Any medication or vaccine (including over-the-counter or prescription medicines, vitamins, and/or herbal supplements) that the participant is receiving at the time of enrollment or receives during the study will be recorded along with:

- Reason for use.
- Dates of administration including start and end dates.
- Dosage information including dose and frequency.

In particular, all pain medication taken on a PRN basis (e.g. paracetamol, up to a maximum of 4,000mg/day; NSAIDs) will be recorded in the dedicated section of eCRF.

In addition, patients will continue to use their regular non PRN pain medication, if taken, (e.g. oxycodone, codeine, botulinum toxin, gabapentin, nortriptyline, muscle relaxants, analgesics) which should remain stable from the 4 weeks prior to randomization visit and at least for the first 4 weeks of the study.

If the patient is using a combination analgesic that contains paracetamol, extreme caution must be exercised in the use of PRN medications containing paracetamol, so as not to exceed a paracetamol total daily dose of 4000 mg (see section 6.5.2)

Medical Monitor should be contacted if there are any questions regarding concomitant or prior therapy.

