10.3. Secondary Efficacy Endpoints

The PGI-C, CGI-C, CGI-S, and MDS-UPDRS will be analysed at weeks 4, 8 and 16 using the same statistical methods i.e. MMRM as for the primary efficacy parameter defined in [Section 10.1](#) by replacing covariate of pain severity at baseline with respective efficacy parameter

Pain severity score at Weeks 4 and 8 will also be analysed by the same MMRM method used for Pain severity score at Week 16 as defined in [Section 10.1](#)

Change from baseline in HADS at Week 16 will be analysed using an ANCOVA. The model will include treatment, baseline HADS and country as fixed effects. The Least Square (LS) means of the change from baseline in HADS score along with the associated SE and 95% CIs will be calculated, and the p-value derived for the difference between treatment groups at Week 16 will be presented.

Percentage of pain responders defined as subjects with reduction in pain severity of ≥ 2 points (“average worst pain experienced in the last 7 days”) as assessed by an 11-point NRS, compared to baseline), will be analysed at weeks 4, 8 and 16 using a Cochran-Mantel-Haenszel adjusted test of the difference in proportions between the two treatment groups. Country will be used as the stratification factor. A 95% confidence interval of the difference in proportions and p-value will be reported. For percentage of pain responders, a missing value at each visit will be imputed to indicate that a subject was a non-responder i.e. a Worst-Case imputation. It will be summarized for both Observed data and Imputed data.

The analysis of amount of concomitant PRN PD pain medications (as reported in the Patient Diary) and concomitant pain drugs (as reported on the ‘Concomitant Medications’ eCRF page) will be summarized in two ways i.e. the number of days on which pain medication was taken in the 7 days preceding Visits at Weeks 4, 8 and 16 and the number of patients taking pain medication in the 7 days preceding Visits at Weeks 4, 8 and 16.

The number of days that pain medication was taken will be analysed using a two-sided Mann Whitney test at the 5% level of significance level to test the null hypothesis of no difference between the two treatments. In case if the patient has not taken any pain medication in the 7

days preceding Visits at Weeks 4, 8 and 16, then the number of days will be considered as zero for that particular patient for that particular visit.

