The percentage of patients using pain medication will be analysed using a Cochran-Mantel-Haenszel (CMH) adjusted test of the difference in proportions between the two treatment groups. Country will be used as the stratification factor. A 95% confidence interval of the difference in proportions and p-value will be reported.

11. Safety Analysis

All analyses of safety will be conducted using the Safety Set.

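### The number of concomitant pain drugs, a listed secondary endpoint, has no efficacy analysis, and a partial cut in regular daily analgesics changes neither measure that SAP 10.3 tests

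*SAP*

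**What the plan says.** The plan describes the pain-drug endpoints in two ways.

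- **Protocol 1.1 and 3 (objectives tables).** Three endpoints serve this objective: "The percentage of reduction in number of concomitant pain drugs from baseline to week 16", the count of patients with any PRN intake, and "Amount of PRN pain medication". No unit is given for the amount.
- **Protocol 9.4.1 and SAP 3.2.** Two endpoints are listed, both on the week before Weeks 4, 8 and 16: the share of subjects whose days of concomitant pain-drug use have fallen, and the number of days with PRN use.

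SAP 10.3 sets the analysis. It covers PRN drugs (from the diary) and concomitant pain drugs (from the Concomitant Medications eCRF page) with two summaries. One is "the number of days on which pain medication was taken in the 7 days preceding Visits at Weeks 4, 8 and 16". The other is a count of users, meaning patients with any such intake during that same week. The first gets a "two-sided Mann Whitney test at the 5% level of significance level". For the second, "The percentage of patients using pain medication will be analysed using a Cochran-Mantel-Haenszel (CMH) adjusted test", stratified by country. Neither test has a baseline term or a change from baseline.

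Protocol 6.5 gives examples of regular drugs ("e.g. oxycodone, codeine, botulinum toxin, gabapentin, nortriptyline, muscle relaxants, analgesics") and asks that they stay stable for at least the first 4 weeks. It requires start and end dates for every medication, and "Dosage information including dose and frequency". SAP 12, which lists changes to the planned analysis, does not mention the pain-drug endpoints.

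**The concern.** The study rationale (Protocol 2.1) cites a post-hoc finding that safinamide cut individual use of pain treatments by about 24%. Protocol 2.3 names lower intake of pain medication as the possible benefit to the patient. A reader of Protocol 3 would expect the report to say whether patients on safinamide needed fewer pain drugs.

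SAP 10.3 does not answer that for regular analgesics. A patient on one or more daily pain drugs has used pain medication on all 7 days of any week until the last drug stops. A real but partial reduction could then appear in the efficacy results as no difference, and a listed endpoint would go unreported with no explanation in SAP 12. Regular regimens may change after Week 4, so Weeks 8 and 16 are where such reductions would be expected.

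**Working it through.** The documents give no figure on this point, so there is none to reproduce. The check has three steps.

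**1. Endpoints against analyses.**

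| Endpoint (paraphrased) | Listed in | Analysis in SAP 10.3 |
|---|---|---|
| Percentage reduction in number of pain drugs, baseline to Week 16 | Protocol 1.1, 3 | None |
| Patients with any PRN intake | Protocol 1.1, 3 | Partly: any use, 7-day window, CMH |
| PRN amount, unit undefined | Protocol 1.1, 3 | Days of use only |
| Share of subjects with fewer days of pain-drug use | Protocol 9.4.1, SAP 3.2 | None: visit values only |
| Days with PRN use | Protocol 9.4.1, SAP 3.2 | Mann-Whitney |

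Protocol 9.4.1 says the pain-drug analysis follows the responder method (country-stratified CMH), which could have covered the fourth row. SAP 10.3 applies the CMH to use, not to reduction in use.

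**2. What a change in regular daily drugs does to the tested measures.** Let D be the number of days out of 7 with at least one pain drug taken; any use is yes if D > 0. Assume that a drug recorded as ongoing and daily counts on all 7 days. The documents do not state this derivation, but it follows from recording by start and end dates.

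| Daily drugs, baseline to visit | Change in number | D | Any use |
|---|---|---|---|
| 3 to 1 | (1 − 3)/3 = −67% | 7 to 7 | yes to yes |
| 2 to 1 | (1 − 2)/2 = −50% | 7 to 7 | yes to yes |
| 1 to 0 | −100% | 7 to 0 | yes to no |

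**3. How much could be missed: an illustration on assumed inputs.** The documents do not give the inputs below, apart from the planned 56 and 28 evaluable patients and the 24% borrowed from the rationale. Assume regular users take 1, 2 or 3 daily drugs in proportions 50%, 30% and 20%. Each drug is stopped independently with probability 24% on active and 0% on placebo.

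- Active users with fewer drugs: 0.5 × 0.24 + 0.3 × (1 − 0.76²) + 0.2 × (1 − 0.76³) = 0.120 + 0.127 + 0.112 = 0.36.
- Active users who reach zero, and so register in D or any use: 0.5 × 0.24 + 0.3 × 0.24² + 0.2 × 0.24³ = 0.120 + 0.017 + 0.003 = 0.14.
- Share of reducers who register: 0.14/0.36 = 39%.

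Simulated power (2,000 runs, two-sided Mann-Whitney at 5%, all 84 patients, non-users at zero):

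| Regular users | Stopping per drug | Change in number of drugs | Days of use at visit, as in SAP 10.3 |
|---|---|---|---|
| 30% | 24% | 24% | 7% |
| 50% | 24% | 81% | 9% |
| 70% | 24% | 99% | 14% |
| 30% | 40% | 71% | 12% |
| 50% | 40% | 99% | 22% |
| 70% | 40% | 100% | 35% |

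The gap has two causes that this comparison does not separate: the 0-or-7 scale and the lack of a baseline comparison.

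**The case against.** The strongest reply is that the SAP follows the protocol's own statistical section: the days-based endpoints stand in Protocol 9.4.1, and SAP 3.2 repeats them. That is right. The protocol contradicts itself and the SAP follows one side, so this is not a simple departure from the protocol. It does not settle the matter, because Protocol 1.1 and 3 still list the other endpoints, and SAP 10.3 also leaves the days-based reduction endpoint untested.

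A second reply is that SAP 8.1 and 8.2 count drugs by arm. They do, so it would be wrong to infer that the report will hold no account of analgesic use. But these are descriptive Safety Set summaries, not by visit, with no change from baseline; 8.1 covers all medication and 8.2 covers PRN drugs only.

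Four stronger readings are tempting, and the documents do not support them.

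- **Only complete stopping of all pain drugs registers.** This holds for regular daily drugs alone. PRN days can take any value from 0 to 7, and SAP 3.2 lists PRN days as a separate endpoint, so a continuing regular drug need not hide a PRN reduction.
- **A lower dose of regular analgesics is a missed protocol endpoint.** No endpoint concerns their dose; amount refers to PRN medication only.
- **Botulinum toxin would score 0 or 1 day.** The derivation is not stated. SAP 8 treats a medication with a missing end date as ongoing, so other scores are possible.
- **A fall in PRN doses per day is recorded but ignored.** Protocol 8.1.1 asks for a daily record of PRN use. Nothing shows that the diary captures intakes or dose per day, and the general dose-and-frequency record in Protocol 6.5 does not establish it.

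**Conclusion.** The concern holds in limited form. The number of concomitant pain drugs, listed in Protocol 1.1 and 3, has no efficacy analysis. The share of subjects with fewer days of use, listed in Protocol 9.4.1 and SAP 3.2, has none either. PRN amount is reduced to days. SAP 12 records none of this. For regular daily analgesics, a cut that stops short of the last drug leaves both tested measures unchanged; this rests on ongoing daily drugs being counted on all 7 days.

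The exact size is at patient level: two drugs to one is −50% in number and 0% in both tested measures. At trial level the size is unknown. The power figures only illustrate it, and they depend on an assumed share of users, drugs per user and stopping rate.

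These are secondary endpoints and the primary analysis is not affected. The gap should still be closed before database lock, because it bears on whether the trial can address its pain-drug objective.

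**What to change.** - **Reconcile the protocol.** Bring Protocol 1.1 and 3 into line with Protocol 9.4.1 and SAP 3.2, so that one set of pain-drug endpoints is defined.
- **Add the number of drugs to SAP 10.3.** Use the Concomitant Medications eCRF page. Analyse the change from baseline to Week 16 in the number of distinct regular pain drugs ongoing, or the percentage of baseline users with fewer drugs by country-stratified CMH. State the denominator, since patients on no regular drug cannot improve, and a rule for switches between drugs.
- **Add the reduction in days.** Analyse the percentage of subjects with fewer days of use than at baseline, as SAP 3.2 already lists. Define the baseline week. If PRN drugs are included, note that Protocol 8 (Visit 1) has PRN intake recorded for the 7 days before baseline, whereas Protocol 8.1.1 starts the PRN record at baseline.
- **PRN amount.** Analyse it in a defined unit only if the diary or eCRF captures intakes or dose.
- **Keep and record.** Keep the planned days-of-use and any-use analyses, and enter the change in SAP 12.

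The cost is SAP wording, programming, and coding work to identify pain drugs among the recorded medications. Drug and dates are already collected. A drug count does not reflect dose or potency: replacing two weak analgesics with one stronger drug would count as a reduction, so the result should be read alongside the days-of-use analyses.

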The screening visit (Visit 1) should take place at least 7 days prior to Visit 2 to allow sufficient time to receive lab results and for subject to complete 7 days' worth of diary data, to fully assess eligibility.

- Obtain written informed consent.
- Record details in IWRS (Section 6.3) for screening number allocation.
- Record demographic data, including age, sex, ethnicity, smoking and alcohol use.
- Record of medical history and PD diagnosis, including Hoehn and Yahr stage.
- Recording of prior medications, concomitant medications (including PRN medication for pain) and therapies (Section 6.5).
- Neurological examination.
- MMSE (Section 8.2.3).
- Physical examination (Section 8.2.1).
- Vital signs (heart rate, systolic and diastolic blood pressure) measured after at least 5 minutes in the supine position (Section 8.2.2).
- Blood sampling for clinical laboratory assessments (haematology and clinical chemistry, including liver function tests) (Section 8.2.4 & 10.2).
- Show the subject how to use the electronic diary (Section 8.1.1).
- Check of inclusion and exclusion criteria (Sections 5.1 and 5.2).

- Issue electronic diary with instructions for the NRS pain assessment and PRN pain medication intake to be completed daily over the seven consecutive days immediately prior to the baseline visit (Visit 2).
- When agreeing the visit schedule with the subject, bear in mind that scales & questionnaires should be done at approximately the same time of day, preferably at least one hour after the usual morning L-Dopa dose (and study medication), when participant is in an optimal ON state.

Visit 2: Baseline visit (Day 1)

At Visit 2, if subject is eligible, the baseline values will be established, and the first dose of study medication will be administered under supervision at the site.

- NRS score of pain intensity > 4 for eligibility, as recorded in the electronic diary. (Section 8.1.1).
- Check of inclusion and exclusion criteria. If participant is eligible, upon completing the data entry in the EDC system the randomization form will appear to randomise subject.
- Vital signs (heart rate, systolic and diastolic blood pressure) measured after at least 5 minutes in the supine position.
- Urine sampling for urine (dipstick) pregnancy test for women of child-bearing potential (WOCB).
- Completion of MDS-UPDRS (part IB and II) and HADS by the subject (Section 8.1).
- Completion of MDS-UPDRS (part IA, III and IV) and CGI-S by the rater (Section 8.1).

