8.1.1. Pain Assessments

The primary efficacy endpoint for the study is the mean change in pain severity ("average pain experienced in the last 7 days"), as assessed by an 11-point NRS, from baseline to week 16.

Pain severity data will be derived from the daily diary.

Daily Diary

An electronic diary will be completed daily by each participant as follows:

- to record the PD pain score at screening (Visit 1), by completion of an 11-point NRS, to confirm eligibility
- the NRS score is calculated over 7 consecutive days immediately prior to baseline (Visit 2/Day 1) and Visits 3, 4 and 5/EOT/ET (Weeks 4, 8 and 16), completion of an 11-point NRS, to allow for the assessment of the average pain experienced in the last 7 days during which patient records on a daily basis the most severe pain using an 11-point NRS.
- on a daily basis from baseline onwards, an accurate record of the use of PRN pain medication for PD-associated pain (Section 10.1.6.2).

Daily Diary Training

At the screening visit, the Investigator (or other trained, qualified personnel) will reinforce recognition of PD-related chronic pain, as well as the use of the daily diary.

On each visit, the Investigator will instruct the participant to complete the daily diary at home for the 7 consecutive days immediately prior to the next visit.

Participants will record the intensity of their PD-associated pain, as the worst pain experienced over the past 24 hours, (from 0 [no pain] to 10 [worst possible pain]) using an 11-point NRS. Pain intensity should be recorded if possible, in the evening before going to sleep. If the subject suffered from more than 1 PD-associated pain, the more severe pain will be documented.

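### PRN pain-medication use is tested without the pre-baseline PRN week that the screening visit asks for: the tests are valid but give up precision

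*SAP*

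**What the plan says.** SAP section 10.3 summarises pain medication in two ways. The first is "the number of days on which pain medication was taken in the 7 days preceding Visits at Weeks 4, 8 and 16", for which it states: "The number of days that pain medication was taken will be analysed using a two-sided Mann Whitney test", at the 5% level. The second is any use in those same windows: "The percentage of patients using pain medication will be analysed using a Cochran-Mantel-Haenszel (CMH) adjusted test of the difference in proportions", and "Country will be used as the stratification factor". No baseline window is defined for either, and no baseline term enters either test. The general baseline rule in SAP section 4 takes the last non-missing evaluation, which does not define a count over 7 days.

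The documents disagree on when PRN recording starts.

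- Protocol section 8, Visit 1 (Screening), issues the diary for the NRS and for "PRN pain medication intake to be completed daily over the seven consecutive days immediately prior to the baseline visit". The Schedule of Activities note, which asks for diary completion in the 7 days before each visit, points the same way.
- Protocol section 8.1.1 asks for PRN use "on a daily basis from baseline onwards, an accurate record of the use of PRN pain medication for PD-associated pain". The protocol synopsis and SAP section 3.1 both start PRN recording at Day 1.

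Other endpoints do use baseline. HADS has a baseline covariate, the MMRM analyses are specified with one, and the responder endpoint is defined against baseline. The primary model also includes regular pain-medication use at baseline.

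**The concern.** If the Visit 1 instruction was followed, the trial holds the same 7-day measure before treatment as at Weeks 4, 8 and 16. A patient's PRN use before treatment plausibly predicts later use, so leaving it out leaves avoidable noise in the treatment comparison. Protocol section 6.3 and SAP section 4.2 name no stratification factor for randomisation, so the design does not balance baseline PRN use either.

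Reduced use of pain drugs is a stated secondary objective, and protocol section 2.3 names it as the possible benefit to patients. With about 84 completers split 2:1, these comparisons have little precision to spare. If some sites or diaries instead followed the passages that start at Day 1 or baseline, the baseline week may be missing for part of the sample. That has to be known before an adjusted analysis is specified.

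**Working it through.** **Inputs from the documents.** Allocation is 2:1, with 105 randomised and 84 completing (56 and 28), and a two-sided 5% level. No effect size, spread or correlation is given for PRN days, and no power is stated for them.

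**The plan's own figure.** The 84 belongs to the primary endpoint. With difference 1, SD 1.5 and 80% power, the normal formula gives (1.96 + 0.842)² × 1.5² × (1 + 1/2) = 26.5, so 27 placebo patients and 81 in all. The t-test version gives 28 and 84, which matches; 84 / 0.80 = 105. So 56 versus 28 is a fair size for checking the PRN test.

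**Formula.** Adjusting for a baseline with correlation ρ multiplies the variance by 1 − ρ². Power then becomes Φ[(1.96 + z) / √(1 − ρ²) − 1.96], where z is the normal quantile of the unadjusted power.

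| Assumed ρ | 1 − ρ² | 84 patients act like | 50% unadjusted power becomes |
|---|---|---|---|
| 0.3 | 0.91 | 92 | 54% |
| 0.5 | 0.75 | 112 | 62% |
| 0.7 | 0.51 | 165 | 78% |

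**Simulation of the actual tests.** 56 versus 28 patients, 2,000 runs per setting. Days out of 7 are binomial, with patient-level logits correlated between baseline and follow-up (logit mean −0.3, SD 1.5). The true difference is about 1 day.

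| Spearman correlation (placebo arm) | Mann-Whitney, raw days | Mann-Whitney, change score | Rank ANCOVA with baseline days |
|---|---|---|---|
| 0.28 | 57% | 41% | 60% |
| 0.50 | 57% | 51% | 68% |
| 0.69 | 55% | 71% | 81% |

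With no true difference, raw Mann-Whitney rejects in 4.4% to 4.6% of runs and rank ANCOVA in 4.4% to 5.2%. A further set of runs at the same size gives raw power of about 57%, rising to 60%, 66% and 77% at correlations of about 0.26, 0.43 and 0.63.

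*Check against the formula at 0.69:* z for 54.9% is 0.123, √(1 − 0.69²) = 0.724, and 2.083 / 0.724 − 1.96 = 0.92, giving 82% against 81% simulated.

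The unadjusted change score does worse than raw days at the two lower correlations, so it is not the right repair.

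**Missing baseline weeks.** By June 2020, 26 patients had completed, and 26 / 105 = 25%. How many lack a baseline PRN week is unknown, so 25% is only an illustration.

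- *Dropping patients without a baseline:* the effective size is n(1 − m) / (1 − ρ²) for missing fraction m, so the gain is gone once m reaches ρ². That is 15% at ρ = 0.39 and 30% at ρ = 0.55.
- *Keeping them with a missing-baseline indicator:* the variance factor is about 1 − 0.75ρ². From 57% raw (z = 0.176), ρ = 0.63 gives 1 − 0.75 × 0.397 = 0.702 and 2.136 / 0.838 − 1.96 = 0.59, or 72%. Simulation gave 59%, 62% and 70% at correlations of about 0.26, 0.43 and 0.63, against 55% to 58% raw.

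The simulations did not include country or regular pain-medication use, and the change to the CMH analysis was not simulated.

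**The case against.** The strongest reply is that nothing in the planned analysis is wrong. The PRN endpoint in SAP section 3.2 is a level, the number of days in the 7 days before each visit. A Mann-Whitney test of that level between randomised arms answers it with a correct error rate. Baseline adjustment is then an efficiency preference, its size rests on an assumed correlation, and rank ANCOVA gives no effect in days. This stands as far as validity goes. It does not remove the loss of precision.

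A reader might go further and infer that the trial cannot show a reduction in PRN use. The documents do not support that: a randomised comparison can show lower use than placebo. What the planned tests cannot give is change from baseline within patients, and the PRN endpoint does not ask for it. The endpoint that does ask for a reduction is the share of subjects with fewer days on concomitant pain drugs. SAP section 10.3 has no analysis for it, but that is a separate gap.

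A reader might also infer that a chance baseline imbalance biases the PRN result. At 56 versus 28, a difference of up to 1.96 × √(1/56 + 1/28) = 0.45 SD lies within the 95% range. The test's 5% error rate already allows for this, so the cost is precision, not bias.

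The late-change objection also has force. Protocol version 3.0 is dated October 2020, and rewording it cannot recover a week that earlier patients never recorded. That calls for a missing-baseline rule; it does not defeat the adjustment.

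**Conclusion.** The point holds as a loss of precision in secondary analyses. At 56 versus 28, and over an assumed baseline-to-follow-up rank correlation of about 0.26 to 0.69, adjusting PRN days for baseline raises power from about 57% to between 60% and 81%, with type I error near 5%. At the low end the gain is about 3 points. With a quarter of baseline weeks missing and an indicator used, some gain remains.

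Three things are not established. That the baseline week is the best predictor of later use is an assumption. That data in hand are being discarded depends on which of the conflicting passages sites followed. The benefit for the comparison of users has not been quantified. The primary endpoint, the sample size and the safety analyses are untouched, and SAP section 10.1 makes no adjustment for multiple comparisons. It is worth doing because it is cheap and uses data that the Visit 1 instructions already request.

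**What to change.** 1. **Settle the baseline week.** Reconcile the protocol's Visit 1 instructions with the synopsis, protocol section 8.1.1 and SAP section 3.1 on when PRN recording starts. Before the SAP is finalised, count blind to treatment how many patients have PRN diary data for the 7 days before Visit 2.
2. **PRN days.** In SAP section 10.3, define baseline PRN days from those 7 diary days. Analyse PRN days at each visit by rank ANCOVA with baseline days, country and regular pain-medication use at baseline, not by an unadjusted change score. Keep patients without a baseline diary through a missing-baseline indicator. State that an uncollected baseline week is missing, not zero, since the SAP counts no recorded use as zero days at the later visits. Report the Mann-Whitney test as supportive, with days summarised by arm so that the effect can be read in days.
3. **PRN users.** Add baseline PRN use (yes/no) to country as an adjustment factor; it does not replace country. Pool sparse country strata by a rule fixed before unblinding.

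The cost is some SAP wording, a protocol clarification and one blinded completeness check. The downsides are the need for a missing-baseline rule, thinner strata in a 2:1 trial of about 105 patients, and little gain if the correlation is low or many baseline diaries are missing.
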